## 2 INTRODUCTION

This Statistical Analysis Plan (SAP) gives details regarding the statistical analyses and data presentation outlined in the final Clinical Investigation Plan (CIP), version A, 07-Sep-2020 for the POWER study (Ref 1.). Any changes from the final CIP are given in Section 8.

## 3 CLINICAL INVESTIGATION DETAILS

### 3.1 Clinical Investigation Objectives

#### 3.1.1 Primary objective

To demonstrate performance through the ability to reduce the number of manual checks in-between changes of absorbing incontinence products using the TENA SmartCare Change Indicator compared to Standard of Care.

#### 3.1.2 Secondary objectives

- Evaluate safety through analyzing device-related adverse events reported during the investigation.
- Evaluate leakage into clothes and/or bed linen.
- Evaluate change in skin redness and irritation.
- Evaluate usability
- Evaluate the number of fecal incidences

### 3.2 Clinical Investigation Design

This is a prospective, interventional, post-market clinical investigation with the aim to demonstrate the performance and safety of the TENA SmartCare Change Indicator when used as intended in subjects affected with Urinary Incontinence (UI) compared to Standard of Care. The outcome will be evaluated and incorporated in the device specific Clinical Evaluation Report (CER) and serve as a base for continuous investigations.

Thirty-five (35) Dependent End Users (DEUs) with UI cared for in a home environment mainly by one Care Giving Relative (CGR) will be recruited in Poland.

The clinical investigation is designed to be conducted in the individuals home environment, for a duration of three (3) weeks + potential incontinence product training week (one) and potential additional days depending on the visit window scheduling. Eight visits are planned for each subject during the duration of the clinical investigation. However, two of the visits are optional and conducted as needed. If considered necessary by the investigator, nurse, or CGR, additional contacts (e.g. visits/phone calls/video calls) can be arranged. The first week will establish an individual baseline for each DEU, during which the number of manual daily checks between changes of the TENA incontinence product are to be registered by the CGR. During the second week the CGR will be provided the TENA SmartCare Change Indicator and learn how to set up and use it as intended by the manufacturer. During the third week the TENA SmartCare Change Indicator will be used as intended by the manufacturer, while the number of additional manual checks between changes of the TENA incontinence product are to be registered by the CGR. The number of manual checks will be analyzed with regard to the individual baseline in order to evaluate the reduction of manual checks.

The overall duration of the investigation is estimated to 8 months, including a 6-month recruitment period. Expected duration of each subject's participation is 3-6 weeks depending on potential incontinence product training week and potential additional days depending on the visit window scheduling.

	
Title: Statistical Analysis Plan
	
Id: Version 2.0_25-Nov-2021

---	---	------------------------------------

### **3.3 Number of Subjects**

The aim is to enroll 35 subjects including a 30% drop-out rate.

### **3.4 Methods of Assigning Subject to Device Groups**

POWER is a post-market, single arm investigation with no planned subgroups analyses. Each participating subject will be provided with the study device; TENA SmartCare Change Indicator (sensor and app). The DEU will act as its own control and documented checks during the investigational week will be compared to the Standard of Care during the baseline week.

### **3.5 Blinding**

Not applicable, as this is a non-randomized single-arm clinical investigation.

## **4 STATISTICAL AND ANALYTICAL PLANS**

If nothing else is stated, descriptive statistics will be given for each variable in the trial. This means number of subjects (n), mean, median, standard deviation (SD), minimum (min) and maximum (max) values will be presented for continuous data and frequencies and percentages for categorical data.

All output from the statistical analysis plan will be part of the Clinical Investigation Report (CIR).

### **4.1 Sample Size Justification**

The sample size calculation is based on the assumption of a reduction of the number of manual checks in-between incontinence product changes by 30%. Based on data from SCA and Ipsos MORI Care Giving Relatives Research - Internal and Client Use (Ref 2.) and the statistical power in section 4.5 this give a sample size of 24 subjects. Assuming a 30% dropout rate, the investigation will include up to 35 subjects. If for any reason the dropout rate should be higher than this, additional subjects might be enrolled in the investigation to reach a total of 24 completed subjects.

### **4.2 Definition of Analysis Sets**

The analysis sets described below will be used for the statistical analysis and presentation of data.

#### **4.2.1 Safety Analysis Set (SAF)**

The SAF will consist of all consented subjects.

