#### **4.2.2 Full Analysis Set (FAS)**

The FAS will include all subjects included in the SAF and have at least one set of efficacy measurements after using the investigational device.

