#### **4.2.4 Use of Analysis Sets**

The presentation of safety data will be based on the SAF.

The presentation of baseline characteristics and demographics will be based on the FAS.

	Title: Statistical Analysis Plan	Id: Version 2.0_25-Nov-2021
---	-------------------------------------	--------------------------------

The primary endpoint analysis will be performed using both the FAS and the PPS. The FAS will be considered as the main analysis.

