**7.3.2 Analyses**

No statistical analyses are planned for safety parameters. The safety endpoint will be summarized using descriptive statistics.

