**7.3.3 Presentation**

**AE/ADE:**

The following summaries of AEs and SAEs will be given:

- Total number of AEs
- Total number of unique AEs
- Total number of unique, related AEs
- Total number (%) of subjects with at least one AE
- Total number (%) of subjects with at least one related AE
- Total number (%) which had AE as reason for premature discontinuation of study device

Severity, action taken, concomitant therapy started and subject outcome of the AEs will be given in data listings only. AEs, which were reason for premature discontinuation of study device, will be listed separately.

Depending on the number of AEs reported, the most frequently reported (e.g. in more than 5% of the patients) AEs might be summarized separately.

The total number of SAEs and patients with a least one SAE will always be given. Further summaries of SAEs depending on the number of SAEs observed.

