**SAE/SADE:**

SAEs/SADEs, if any, will be listed only.

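### The safety set is everyone who consented, so subjects lost before Visit 3 dilute the device-discontinuation percentage without ever having had the Change Indicator

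*SAP*

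**What the plan says.** SAP 4.2.1 defines the safety set by consent alone: "The SAF will consist of all consented subjects". SAP 4.2.4 then applies it without exception: "The presentation of safety data will be based on the SAF". SAP 7.3.3 lists the summaries, including "Total number (%) which had AE as reason for premature discontinuation of study device" and "Total number (%) of subjects with at least one related AE". SAP 7.3.2 makes all of this descriptive: "No statistical analyses are planned for safety parameters".

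The protocol (CIP) fixes the timing. Under CIP 10.5.1.1 and 10.5.1.2, a subject is enrolled once consent is signed, and eligibility is confirmed afterwards. CIP 10.5.1.4 places the first handover of the Change Indicator at Visit 3, after the baseline week. SAP 6.1 names the Change Indicator as the active treatment, and SAP 6.3 puts planned exposure at two weeks.

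The only other set that looks beyond consent is the FAS, whose members must "have at least one set of efficacy measurements after using the investigational device". SAP 4.2.4 does not assign the FAS to safety.

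**The concern.** A percentage of subjects who discontinued a device is meaningful only among those who had it. With an all-consented denominator, early leavers can enter only the bottom of the fraction. Any distortion therefore goes one way, towards a smaller apparent device risk.

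The mismatch also touches the protocol's own safety question. The Synopsis asks about events related to the Change Indicator, and CIP 10.1.2 sets the adverse event endpoint in weeks 2 and 3, when the device is in use. SAP 7.3 restates the endpoint without that window, while SAP 8 declares no changes from the CIP, so the window still applies. A percentage of all consented subjects can be computed correctly and still answer a different question. The results are meant to feed the Clinical Evaluation Report (CIP 5.1, SAP 3.2).

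**Working it through.** **Planned number.** SAP 4.1 gives 24 evaluable subjects and 30% dropout: 24 / (1 − 0.30) = 34.3, rounded up to 35. The plan's figure is reproduced, and it implies up to 35 − 24 = 11 losses.

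**Time from consent to handover** (CIP Table 2):
- Consent at Visit 1: Day 0 to Day 8 = 8 days, or more with the visit window.
- Consent at Visit 0: Day −7 to Day 8 = 15 days, or about that with the windows.

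**Dilution.** Let N be the number consented, k the number lost before Visit 3 and x the number with the event.
- Reported percentage: x / N
- Percentage of device recipients: x / (N − k)
- Ratio of the first to the second: (N − k) / N

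The documents give no value for k. I assume N = 35 and take k from 0 to 11. The upper end means that all planned loss falls before handover.

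| k | Exposed | Factor | x = 1: reported vs exposed | x = 2: reported vs exposed |
|---|---|---|---|---|
| 0 | 35 | 35/35 = 1.00 | 2.86% vs 2.86% | 5.71% vs 5.71% |
| 5 | 30 | 30/35 = 0.86 | 2.86% vs 3.33% | 5.71% vs 6.67% |
| 11 | 24 | 24/35 = 0.69 | 2.86% vs 4.17% | 5.71% vs 8.33% |

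For one event the gap is 0, 0.48 or 1.31 percentage points. In relative terms the understatement is at most 1 − 0.686 = 31%. Because SAP 4.1 allows extra enrolment if dropout exceeds 30%, 0.69 is the extreme only under the planned loss.

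**Frequent-event line.** SAP 7.3.3 says that "the most frequently reported (e.g. in more than 5% of the patients) AEs might be summarized separately". One subject in 20 is exactly 5.0%, which is not above the line. Two in 39 is 5.13%, which is. Two subjects are therefore needed for every denominator from 20 to 39, and the line does not move within the range above.

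**Screening failures.** CIP 10.3.4 describes the 35 as meeting all criteria. SAP 3.3 speaks of enrolling 35, and CIP 10.5.1.2 counts a subject as enrolled from consent. It is not settled whether screening failures fall inside the 35 or on top of it, so I give no figure for them.

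**Which percentages are affected.** The device-discontinuation percentage carries the full factor. The related-event percentage carries it only if *related* means related to the Change Indicator. SAP 7.3.3 does not say, and CIP 19.2 and 19.2.2 also assess relationship to procedures. If procedures or the TENA absorbing product are included, subjects are at risk before handover and the factor does not strictly apply.

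**The case against.** The strongest defence is that an all-consented set fits the way events are collected. CIP 19.2 monitors from enrolment, TENA absorbing products are supplied from Visit 0 or 1, and procedure-related events can occur before Visit 3. For the percentage with any adverse event over the whole study, all consented subjects is a sensible denominator. That stands, and it is why the set should be kept for pre-handover events. It does not help the device-discontinuation line, where no event is possible before handover.

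A second argument is that the device-discontinuation line names no denominator of its own. That is true, but SAP 4.2.4 supplies one for all safety data, so the plan does state a rule.

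Third, the exposed figure can largely be recovered. SAP 5.1 reports subjects at each visit. SAP 9 promises listings of exposure, discontinuations and adverse events, and SAP 7.3.3 lists events that led to stopping the device separately. For serious events, "SAEs/SADEs, if any, will be listed only", so the listing needs no denominator. This limits the harm. It also shows that the data for the correct percentage already exist.

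Fourth, the effect may be nil. CIP 8.2 anticipates no device effects, and zero events give 0% on either denominator. That is right, but the denominator matters as soon as one event occurs and is better fixed before the data are seen.

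Finally, a subject who receives the device but never uses it would still dilute a percentage based on receipt. That is a fair refinement, which the SAP can settle in a sentence. It does not justify including people who were never given the device.

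**Conclusion.** The concern holds. SAP 4.2.1 and 4.2.4 put subjects who never had the Change Indicator into the denominator of a percentage about stopping it, and no other set is assigned to correct this. With 35 consented, the reported figure is between 1.00 and 0.69 times the figure among recipients, depending wholly on assumed losses before Visit 3. One event differs by 0 to 1.3 percentage points. The related-event percentage is affected to the same extent only if *related* means related to the Change Indicator.

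No hypothesis test, pass/fail criterion or primary analysis changes. This is a worthwhile, inexpensive correction to descriptive reporting. It is not a threat to the trial's main conclusion.

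**What to change.** In SAP 4.2, define a device-exposed set of subjects who received the Change Indicator at Visit 3, and say how a subject with no registered use is treated (SAP 6.4 already looks at use recorded in the device system). In SAP 7.3.3, use that set as the denominator for the device-related event percentage, the device-discontinuation percentage and the week 2-3 incidence required by CIP 10.1.2. State that *related* in these lines means related to the Change Indicator.

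Keep the all-consented set for listing events from consent to handover, so that no recorded event is lost. The SAE/SADE listings and the FAS can stay as they are.

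The cost is a little SAP wording and one extra listing from data already collected. If anyone leaves before Visit 3, the reported percentages become slightly less favourable. If nobody does, they are unchanged.

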#### **4.2.2 Full Analysis Set (FAS)**

The FAS will include all subjects included in the SAF and have at least one set of efficacy measurements after using the investigational device.

#### **4.2.3 Per Protocol Set (PPS)**

The PPS will include all subjects included in the FAS who:

- Do not have any other major CIP deviations, which will affect the assessment of efficacy.

The final criteria for the PPS, regarding which CIP deviations that warrant exclusions, will be determined when all data on CIP deviations are available and before any statistical analysis has taken place.

#### **4.2.4 Use of Analysis Sets**

The presentation of safety data will be based on the SAF.

The presentation of baseline characteristics and demographics will be based on the FAS.

	Title: Statistical Analysis Plan	Id: Version 2.0_25-Nov-2021
---	-------------------------------------	--------------------------------

The primary endpoint analysis will be performed using both the FAS and the PPS. The FAS will be considered as the main analysis.

#### **4.3 Definition of Baseline**

The first week will establish an individual baseline for each DEU, during which the number of manual checks between changes of the TENA incontinence product are to be registered continuously in a diary by the CGR.

#### **4.4 Summary Statistics**

In general, all data collected will be presented with summary statistics and given in patient data listings (an overview of patient data listings are given in Section 9). Summary statistics will include number of patients, mean, standard deviation, median, minimum and maximum for continuous data and frequency and percentage for categorical data.

#### **4.5 Significance Level and Power**

All statistical testing will be performed at the 5% significance level. The level of statistical power is set to 90% for the primary endpoint.

#### **4.6 Multiple Comparisons/Multiplicity**

No adjustment for multiplicity of testing will be done. There will be one formal statistical analysis (primary efficacy endpoint) in line with the sample size determination. All other statistical tests will be considered as descriptive.

#### **4.7 Handling of Drop-outs, Missing Data and Outliers**

Outliers will be included in summary tables and listings, and will not be handled separately. Available data from prematurely withdrawn subjects will be included in the analysis as far as possible. Missing data will not be imputed.

#### **4.8 Adjustment for Covariates**

Not applicable.

#### **4.9 Multicenter Studies**

Not applicable.

#### **4.10 Examination of Subgroups**

No examination of subgroups is planned.

#### **4.11 Blind Review**

Not applicable, as this is a non-randomized single-arm clinical investigation.

### **5 SUBJECTS**

#### **5.1 Subject Disposition**

The number of subjects that entered the study, withdrawn subjects, completed subjects and the number of subjects at each visit will be summarized.

#### **5.2 Baseline Characteristics and Demographics**

The following baseline characteristics will be given in total:

- Age
- Gender
- Evaluation of general cognitive function
- Ghent Global IAD Categorisation Tool - GLOBIAD score

Medical history, physical examination, concomitant medication, urine pregnancy test collected at visit 1 (screening) will be listed only.

	
Title: Statistical Analysis Plan
	
Id: Version 2.0_25-Nov-2021

---	---	------------------------------------

## 6 TREATMENT INFORMATION AND EXTENT OF EXPOSURE

### 6.1 Active Treatment

Active treatment in this study is the use of TENA SmartCare Change Indicator (sensor and app).

### 6.2 Placebo Treatment

Not applicable as no placebo treatment is involved.

### 6.3 Extent of Exposure

The exposure of study devices for each subject is estimated to 2 weeks.

### 6.4 Compliance of Study Device

Compliance of the study device will be determined by observing that the devices are being used as is registered in the device system.

### 6.5 Concomitant Medications

Subjects are allowed to continue their regular medication during the study. Relevant concomitant medication data will be listed only.

## 7 STATISTICAL METHODOLOGY

All efficacy parameters will be presented using summary statistics. Additional statistical analyses are specified below.

### 7.1 Primary efficacy endpoint

#### 7.1.1 Definition

The primary efficacy endpoint is the change in percentage of the number of manual checks between week 1 and week 3 of the investigation. The average manual checks/day for a subject week will be used for the percentage calculation, since data may be available for less or more than 7 days.

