9.3 Hypothesis

The null hypothesis (H_0) is that there is no difference in the mean number of checks performed during the investigation week compared to the baseline week.

The alternate hypothesis (H_1) is that there is a reduction in the mean number of checks performed during the investigation week compared to the baseline week.

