10.1.1 Primary Endpoint

- Change in the number of manual checks in-between the daily changes of the absorbing incontinence product at week 3 (investigational week) compared to week 1 (baseline week).

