10.3 Subjects

10.3.1 Inclusion Criteria

The DEUs and/or CGRs must meet all of the following criteria to be eligible for this clinical investigation:

1. DEU is diagnosed with urinary incontinence managed with a tape-style incontinence product.
2. DEU is unable to sufficiently communicate the need for an incontinence product to be changed.
3. DEU is being cared for in a home environment and most of the care is provided by a main CGR.
4. DEU is willing and able to provide informed consent and to participate in the clinical investigation or has a legally designated representative willing to provide informed consent on behalf of the DEU. Note, the legally designated representative and main CGR cannot be the same person.
5. CGR is willing and able to provide informed consent to participate in the clinical investigation.
6. The CGR frequently checks the saturation level of the incontinence product, manually and/or by a touch-feel process.
7. If incontinence is managed by pharmaceuticals, the dose regime is stable.
8. DEU and CGR ≥ 18 years of age.

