12 STATISTICAL CONSIDERATIONS

12.1 Statistical design, method and analytical procedures

If nothing else is stated, descriptive statistics will be given for each variable in the trial. This means number of subjects (n), mean, median, standard deviation (SD), minimum (min) and maximum (max) values will be presented for continuous data and frequencies and percentages for categorical data. The level of significance is similar for all variables and specified in section 12.3. The primary variable is the percentage change of the number of manual checks between week 1 and week 3 of the trial. A one-tailed paired t-test will be used to test if the number of manual checks have been reduced relative to week 1. If the variable is not normally distributed the non-parametric Wilcoxon signed-rank test will be used and in case of a significant result, a one-sided 95% confidence interval will be constructed for the percentage change in checks between week 1 and week 3 to validate at least a 30% reduction.

For the secondary variable change in number of leakages between week 1 and week 3. The analysis is to determine if there is a significant difference in leakages. A paired t-test will be used for comparison. If the variable is not normally distributed a non-parametric Wilcoxon signed rank test will be used.

The secondary variable change in skin redness/irritation between week 1 and 3. This variable is evaluated using the Ghent Global IAD Categorisation Tool (GLOBIAD) [19]. GLOBIAD is a categorisation tool to monitor IAD prevalence and incidence. IADs can be scored as 1A, 1B, 2A and 2B. The analysis is to determine if there is a significant difference in scoring between the time points. A paired t-test will be used for comparison. If the variable is not normally distributed a non-parametric Wilcoxon signed rank test will be used. For this variable it is possible we cannot detect any difference due to the short time period.

For the secondary variable number of fecal incidences per week in the trial, the analysis is to determine if there is significant difference in incidences per week. A non-parametric Wilcoxon signed rank test will be used for comparison.

There are also safety and usability endpoints in the trial however these are only to be covered by descriptive and summary statistics.

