#### 7.1.2 Analysis

A one-tailed paired t-test will be used to test if the number of manual checks has been reduced relative to week 1. If the variable is not normally distributed the non-parametric Wilcoxon signed-rank test will be used and in case of a significant result, a one-sided 95% confidence interval will be constructed for the percentage change in checks between week 1 and week 3 to validate at least a 30% reduction. The Shapiro-Wilk test will be used to test normality.

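### The primary decision is written on two scales, mean number of checks and percentage change, with no estimator named for the 30% step, and the two scales can give opposite pass/fail answers

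*SAP*

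**What the plan says.** **Count scale.** Under protocol 9.3 the null hypothesis is that "there is no difference in the mean number of checks performed during the investigation week compared to the baseline week", and the alternative is that "there is a reduction in the mean number of checks performed during the investigation week compared to the baseline week". The endpoint in protocol 10.1.1 is also a change in number: "Change in the number of manual checks in-between the daily changes of the absorbing incontinence product at week 3". The test in SAP 7.1.2 is worded the same way: "A one-tailed paired t-test will be used to test if the number of manual checks has been reduced relative to week 1".

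**Percentage scale.** Protocol 12.1 states: "The primary variable is the percentage change of the number of manual checks between week 1 and week 3 of the trial". SAP 7.1.1 agrees: "The primary efficacy endpoint is the change in percentage of the number of manual checks between week 1 and week 3 of the investigation". It then fixes the unit: "The average manual checks/day for a subject week will be used for the percentage calculation".

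**The 30% step.** SAP 7.1.2 provides for a Shapiro-Wilk check, a Wilcoxon signed-rank test if normality fails and, after a significant result, a one-sided 95% confidence interval for the percentage change to confirm at least a 30% reduction. Protocol 12.5 makes a reduction of more than 30% the pass/fail criterion.

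**Not stated.** The documents do not say whether the percentage is a mean or median of individual changes or a ratio of group means, which variable Shapiro-Wilk examines, or which interval follows the Wilcoxon test. SAP section 8 reports no changes from the protocol.

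**The concern.** A percentage of averages and an average of percentages are different quantities. The first weights subjects by how often they are checked; the second weights them equally. They differ whenever the relative effect varies with the baseline rate.

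The second also divides by a one-week baseline that carries noise. A low week 1 inflates that subject's ratio more than an equally high week 1 deflates it, so the mean ratio is pushed upward. A fall cannot exceed 100%, but a rise has no ceiling. Inclusion criterion 6 ("The CGR frequently checks the saturation level of the incontinence product, manually and/or by a touch-feel process") sets no numerical minimum, and both documents leave outliers without separate handling.

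SAP 4.6 makes this the only formal analysis, and the 30% answer is the pass/fail result. With the estimator open, a choice made after the data are seen could decide that result.

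**Working it through.** **1. The plan's own figure.** 24 / (1 - 0.30) = 34.3, rounded up to 35, which agrees. The 24 cannot be reproduced, because no SD is given on either scale. Working backwards for a 30-point change, 90% power and one-sided 5%: SD = 30 x √24 / (1.645 + 1.282) ≈ 50 percentage points (48-49 with the t distribution). So the sample size does not reveal the intended scale.

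**2. Contradiction by arithmetic.** Take 24 subjects, 12 at 12 checks/day and 12 at 3, so the baseline mean is 7.5. The t quantile (23 df, one-sided 95%) is 1.714.

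| | A: heavy -50%, light 0% | B: heavy -15%, light -70% |
|---|---|---|
| Week 3, heavy / light | 6 / 3 | 10.2 / 0.9 |
| Week 3 mean | 4.5 | 5.55 |
| Change in mean checks | 4.5/7.5 - 1 = -40% | 5.55/7.5 - 1 = -26% |
| Mean of percentages | (-50 + 0)/2 = -25% | (-15 - 70)/2 = -42.5% |
| SD of percentages | 25.5 | 28.1 |
| Upper 95% limit | -25 + 1.714 x 25.5/√24 = -16% | -42.5 + 1.714 x 28.1/√24 = -32.7% |
| 30% step on percentages | fail | pass |
| Week 3 - 0.70 x week 1, heavy / light | -2.4 / +0.9 | +1.8 / -1.2 |
| Mean (SD); t | -0.75 (1.69); -2.18 | +0.30 (1.53); +0.96 |
| 30% step on mean checks | pass | fail |

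In A the paired t-test on counts gives p < 0.0001.

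These two-point data would fail Shapiro-Wilk, so I also take the rank route on percentages. Deviations from -30% in A are 12 at -20 and 12 at +30. The mean ranks are 6.5 and 18.5, so the rank sums are 78 negative and 222 positive: fail. In B they are 12 at +15 and 12 at -40, giving 222 negative and 78 positive. With the tie-corrected variance 24 x 25 x 49/24 - 2 x (12³ - 12)/48 = 1153.5, z = (222 - 150)/√1153.5 = 2.12, one-sided p ≈ 0.017: pass. Both contradictions survive the fallback.

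**3. Size under a uniform effect.** Inputs:
- Baseline 8.75 checks/day = 2.5 checks per change x 3.5 changes per day, the midpoints of the ranges in protocol 5.1.
- Between-caregiver CV 0.6 and week-to-week CV 0.2, 0.3 or 0.4: assumptions, since the documents give no variance.
- Poisson counts over 7 days; week-to-week noise independent between the two weeks (assumption).

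For a true reduction r, the mean ratio is roughly (1 - r) x (1 + CV² + c), where c = (1 + 0.6²)/(7 x 8.75) = 0.022 is the Poisson part. With r = 0.45:
- CV 0.2: 0.55 x 1.062 = 0.584, a 42% fall.
- CV 0.3: 0.55 x 1.112 = 0.612, a 39% fall.
- CV 0.4: 0.55 x 1.182 = 0.650, a 35% fall.

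Simulation (20,000 trials, N=24) gives 41, 38 and 34%. A true 45% is used because at exactly 30% a valid version should pass only about 5% of the time.

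| Share of trials clearing the 30% bound, true 45% fall | CV 0.2 | CV 0.3 | CV 0.4 |
|---|---|---|---|
| Mean of percentages, t limit | 73% | 40% | 21% |
| Same, with Shapiro-Wilk/Wilcoxon branch on percentages | 81% | 54% | 34-36% |
| Ratio of means (t-test of week 3 - 0.70 x week 1) | 91% | 70% | 53% |

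At a true 30% fall the mean of percentages passes in about 0.6-1.5% of trials and the ratio of means in about 5%.

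**The case against.** Four points on the other side carry weight.

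**The average of percentages is inferred.** SAP 7.1.1 defines a subject-level percentage; no passage says that these are averaged. Because protocol 12.1 names percentage change just before the t-test sentence, a t-test on percentages is also a possible reading, and would put test and interval on one scale. This stands. A reader might infer that the plan commits itself to the arithmetic mean of percentages, but the documents leave the estimator open. Even on that reading, protocol 9.3 still speaks of the mean number of checks.

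**Extreme examples prove less than they seem to.** If 20 caregivers go from 10 to 6 checks/day and 4 go from 1 to 3, mean checks fall 35% (8.5 to 5.5) while the mean percentage change is 0%. But Shapiro-Wilk rejects there (p = 2e-8), so the planned test would be Wilcoxon, and the median and Hodges-Lehmann percentage changes are both -40%. One check a day also sits badly with the requirement for frequent checking and with the 6-12 checks/day implied by protocol 5.1. So that case shows under-specification, not a fixed contradiction. Examples A and B do not depend on the branch.

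**The loss depends on assumptions.** Correlation of 0.5 between a caregiver's two weeks raises passing for the mean of percentages to about 88, 68 and 46%. With Poisson noise alone it passes about 98% of the time, with bias of about 1 point. The gap to the ratio of means narrows but does not close.

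**Individual percentages suit a design in which each subject is its own control.** This is fair. The ratio of means is not the only valid choice.

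**Conclusion.** The inconsistency is on the page: one primary decision, two scales, no named estimator. That finding needs no assumed variance. At n=24 the scales can disagree on the 30% question both ways (-40% against -25%, and -26% against -42.5%).

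A reader might infer that the percentage version always understates the device. The documents do not support that. Understatement follows from a uniform relative effect with independent weekly noise. Positive correlation between weeks shrinks it, and proportionally larger reductions in light checkers can reverse it, as in B. Where effects vary with baseline, the two summaries are different estimands and neither is simply biased.

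Nor do the documents support a general charge of inflated false success. With a uniform 30% fall the mean of percentages is conservative; a pass on percentages with less than a 30% fall in mean checks needs effects that differ by baseline.

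In the uniform case the cost is power: about 73/40/21% against 91/70/53%, or 81/54/34-36% with the normality branch, all conditional on the assumed CVs. Severity: should-fix, settled before any outcome data are examined.

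**What to change.** Use one estimand in the hypothesis, test, interval and pass/fail rule.

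**To match protocol 9.3.** In SAP 7.1.1 define the reduction as 1 - (mean week-3 checks/day ÷ mean week-1 checks/day) over the FAS. In SAP 7.1.2:
- Test week 3 - week 1, one-sided at 5%.
- If significant, test week 3 - 0.70 x week 1, one-sided at 5%, and report the matching one-sided 95% limit for the ratio: the value R at which the test of week 3 - R x week 1 gives p = 0.05.
- Tabulate individual percentage changes descriptively.

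**If a within-subject relative change is preferred.** Restate the hypothesis on that scale. Use the mean log ratio, with a stated rule for zero counts, or the Hodges-Lehmann estimate, each with its matching one-sided limit against 30%. Do not use the arithmetic mean of percentages.

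Either way, name the variable that any Shapiro-Wilk test examines and the interval used in each branch, state the SD and scale behind N=24, and record the change in SAP section 8.

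**Cost.** SAP wording and a few program lines, plus a change to protocol 9.3 under the second option. With the ratio of means, heavy checkers weigh more, which is what a hypothesis on the mean number implies. With the within-subject option, the result no longer describes the fall in total checks.
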